### 9.1.2 Serious Adverse Event

An SAE is defined as any adverse experience occurring at any dose of study medication that occurs between the time the patient signs the informed consent form through the end-of-study that results in any of the following outcomes:

- Death
- Life-threatening situation (patient is at immediate risk of death)
- In-patient hospitalization or prolongation of existing hospitalization for a clinically relevant reason (note that this excludes “social” hospitalization for nonmedical causes such as lack of transportation to home)
- Persistent or significant disability/incapacity
- Congenital anomaly/birth defect in the offspring of a patient who received study drug
- Important medical events that may not result in death, be life-threatening, or require hospitalization may be considered serious when, based upon appropriate medical judgment, they may jeopardize the patient or patient may require medical or surgical intervention to prevent one of the outcomes listed in this definition. Examples may include, but are not limited to:
  - Intensive treatment in an emergency room or at home for allergic bronchospasm
  - Blood dyscrasias that do not result in hospitalization
  - Seizures that do not result in hospitalization

A hospitalization meeting the regulatory definition for “serious” is any in-patient hospital admission that includes a minimum of an overnight stay in a health care facility.

Worsening and/or flares of EPI disease activity should be recorded in the appropriate EPI CRF. However, if disease worsening meets any of the criteria for an SAE, then it must be recorded on the SAE form and reported to the Sponsor or designee within 24 hours of becoming aware of the event.

### 9.1.3 “Serious” vs “Severe” Adverse Event

To avoid confusion or misunderstanding over the difference between the terms “serious” and “severe,” which are not synonymous, the following note of clarification is provided (excerpted from International Council for Harmonisation [ICH] E2A):

The term “severe” is often used to describe the intensity (severity) of a specific event (as in mild, moderate, or severe myocardial infarction); the event itself, however, may be of relatively minor medical significance (such as severe headache). This is not the same as “serious,” which is based on patient/event outcome or action criteria usually associated with events that pose a threat to a patient’s life or functioning. Seriousness (not severity) serves as a guide for defining regulatory reporting obligations.

### 9.1.4 SAE Definition Clarifications

- Death is an outcome of an AE, and not an AE in itself.
- All deaths during study through the end-of-study, regardless of cause or relationship, must be reported.
- “Occurring at any dose” does not imply that the patient is actively receiving study drug at the time of the event.
- “Life-threatening” means that the patient was at immediate risk of death from the event as it occurred. This does not include an event that might have led to death, had it occurred with greater severity.
- Complications that occur during hospitalizations are AEs. If an AE prolongs hospitalization, it is an SAE.
- “In-patient hospitalization” means the patient has been formally admitted to a hospital for medical reasons, for any length of time, excepting situations where an untoward medical occurrence has not occurred (e.g., hospitalization for elective surgery, social, or convenience admissions). Hospitalization may or may not be overnight. It does not include presentation and care within an emergency department (although an emergency department visit may define a medically important event, which is also considered an SAE).

- If any AE worsens during the study and eventually meets the criteria for an SAE the AE should be recorded as a new SAE.

## 9.2 Reporting Procedures for All Adverse Events

AEs will be recorded in the CRF for all patients from the time the patient signs the informed consent form through the end of the study or patient withdrawal.

The Investigator is responsible for ensuring that all AEs (as defined in [Section 9.1](#) and as further specified below) observed by the Investigator or reported by patients are collected and recorded in the patients' medical records, in the CRF, and as an SAE in the electronic data capture system. These AEs will include the following:

1. All SAEs (as defined in [Section 9.1.2](#)) that occur.
2. All nonserious AEs (as defined in [Section 9.1.1](#)) that occur.

The following AE attributes must be assigned by the Investigator:

- AE diagnosis or syndrome(s) (if known, signs or symptoms if not known);
- event description (with detail appropriate to the event);
- dates of onset and resolution; severity; assessment of relatedness to study drug; and
- action taken with study medication.

The Investigator may be asked to provide follow-up information, discharge summaries, and extracts from medical records or CRFs.

It will be left to the Investigator's clinical judgment to determine whether the relatedness of an AE, and of sufficient severity to require the patient's removal from treatment or from the study. A patient may also voluntarily withdraw from treatment because of what he or she perceives as an intolerable AE. If either of these situations arises, the patient should be strongly encouraged to complete the End-of-Therapy assessments and be under medical supervision until symptoms cease or the condition becomes stable.

## 9.3 Grading of Adverse Events,

The Investigator will be asked to provide an assessment of the severity of the AE using the categories noted below. This assessment is subjective, and the Investigator should use medical judgment to compare the reported AE to similar events observed in clinical practice. It is important to recognize that severity is not equivalent to event seriousness.

---

Grade 1 (Mild): usually transient; requires no special treatment and does not generally interfere with the patient's daily activities.

Grade 2 (Moderate): produces a mild to moderate level of inconvenience to the patient and may interfere with daily activities. These events are usually ameliorated by simple therapeutic measures.

Grade 3 (Severe): significantly interrupts daily activity and requires systemic drug therapy or other medical treatment.

#### **9.4 Relationship to Study Drug**

For each reported AE, the Investigator must make an assessment of the relationship of the event to the study drug using the following scale:

Unrelated: The event is definitely not or unlikely associated with study drug administration and is judged because of causes other than the study drug.

Related: Events considered to be related are those that follow a reasonable temporal sequence from administration of the study drug, that are not easily explained by another cause such as known characteristics of the patient's clinical state or other treatment or confirmed by improvement on stopping or slowing administration of the study agent (de-challenge), if applicable.

#### **9.5 Serious Adverse Event Reporting Procedures**

Serious adverse events will be recorded from the time the patient signs the informed consent form through the end of study. AEs will be followed until the event resolves or stabilizes, or until the end of study for that patient.

If the AE is an SAE and is assessed as "related to study drug", it must be followed until either the event is considered stable or resolved.

Any SAE assessed as "unrelated to study drug" will be followed as clinically indicated until its resolution or, if not resolving, until considered stable or until the final study visit for that patient whichever comes first.

All SAEs that occur must be reported within 24 hours of discovery or notification of the event. Initial SAE information and all amendments or additions must be recorded as an SAE in the electronic data capture system and sent to the Sponsor or designee.

If a patient is permanently withdrawn from the study because of an SAE, then this information must be captured as an SAE in the initial or follow-up electronic data capture record as well as the End-of-Therapy CRF.

The Investigator should notify the appropriate IEC/IRB of SAEs occurring at the site and other SAE reports received from AzurRx, in accordance with local procedures and statutes.

AzurRx will ensure that applicable regulatory authorities receive all relevant information on an SAE, in accordance with regulatory requirements. Results of AzurRx's investigation of other safety information shall be submitted, as required.

## **9.6 Pregnancy Reporting Procedures**

Patients must be instructed to inform the Investigator immediately if they or their partners become pregnant after the patient has received their first dose of investigational product during the study. The following actions should be taken in the event of a confirmed pregnancy:

1. For female patients, study drug should be discontinued immediately.
2. The pregnancy should be reported to the Safety Group within 24 hours of notification using the applicable Pregnancy Report Form.
3. The Investigator should counsel the patient regarding the possible effects of previous study drug exposure on the fetus and the need to inform the study site of the outcome of the pregnancy.
4. The patient or the patient's pregnant partner must be monitored until the immediate postnatal period or until termination of the pregnancy. The outcome should be reported to the Medical Monitor using the Pregnancy Outcome Form.

Pregnancy is not an AE in and of itself. However, any pregnancy complications or elective terminations of a pregnancy for medical reasons will be recorded as an AE or SAE. A spontaneous abortion is always considered an SAE and will be reported as described in the AE and SAE sections (Section 9.2 and Section 9.5). Furthermore, any SAE occurring as an adverse pregnancy outcome poststudy must be reported to the Medical Monitor.

## **9.7 Hepatic Monitoring**

The following guidelines are provided for the management of serum transaminase elevations in patients with new, clinically meaningful increases in liver function tests occurring during the study. All cases of new (i.e., since screening) elevations in ALT or AST  $\geq 3$  times ULN or any questions concerning the management of a patient with elevated serum transaminases should be discussed with the study Medical Monitor.

---

---

Patients who experience a new (i.e., since screening) elevation in ALT or AST level to  $\geq 3 \times \text{ULN}$  OR total bilirubin  $\geq 1.5 \times \text{ULN}$  will have hepatic monitoring (ALT, AST, Bilirubin) until one of the following occurs:

- Withdrawal from study if elevation in ALT or AST level to  $\geq 3 \times \text{ULN}$  is associated with a rise in total serum bilirubin to  $\geq 2 \times \text{ULN}$  (without laboratory findings of cholestasis [elevated serum alkaline phosphatase  $\geq 2 \times \text{ULN}$ ])
- Withdrawal from study if elevation in ALT or AST level to  $\geq 5 \times \text{ULN}$  is associated with new or exacerbated gastrointestinal (GI) symptoms (i.e., nausea, vomiting, right upper quadrant pain, and/or jaundice) and other causes are not evident
- Withdrawal from the study if elevation in ALT or AST is  $\geq 10 \times \text{ULN}$  regardless of serum bilirubin level

Causes of acute elevation of transaminases should be considered and ruled out (e.g., viral hepatitis, concomitant medications).

Patients discontinued from study drug administration should resume porcine PERT therapy according to physician prescription.

## **9.8 Data Safety Monitoring Board**

An external, independent data safety monitoring board (DSMB) will monitor and protect the safety and risk/benefit of the study patients throughout the study duration and evaluate the risk/benefit of study drug. The DSMB will consist of suitably qualified individuals, including CF experts.

## **9.9 Appropriateness of Measurements**

The efficacy and safety assessments planned for this study are widely used and generally recognized as reliable, accurate, and relevant to the assessment of biological products administered to patients with CF.

## 10. STATISTICAL METHODS

### 10.1 General Considerations

**The statistical methods will be further detailed in the Statistical Analysis Plan (SAP).**

Any change to the data analysis methods described in the protocol will require an amendment only if it changes a principal feature of the protocol. Any other change to the data analysis methods described in the protocol, and the description for making the change, will be described in the SAP and in the clinical study report. Additional exploratory analyses of the data will be conducted as deemed appropriate.

Statistical methodology and analyses will be in accordance with the principles outlined by the International Council for Harmonisation (ICH) E9 guidelines.

Tables, listings, and figures will be produced in accordance with the principles outlined by the ICH E3 guidelines.

Summaries will consist of descriptive statistics including the nonmissing counts, mean, standard deviation, median, Interquartiles (IQ), minimum and maximum values for continuous variables, and number and percentage of patients in each defined category for categorical variables.

The primary efficacy endpoint analysis aims to compare the mean CFA after receiving MS1819 vs porcine PERT. With the sample size to be employed, primary efficacy analysis will be descriptive rather than inferential.

As a general rule, missing data will not be replaced.

### 10.2 Sample Size Determination

Based upon CFA data obtained in the recently completed Phase 2a trial (OPTION), 15 patients per MS1819 dose should provide sufficient point estimates of CFA in each group. Given the acceptable safety profile obtained in the OPTION trial, a sample of 15 patients should be adequate for observation of safety per dose of MS1819. This study will use descriptive analyses for both safety and efficacy analyses.

### 10.3 Analysis Sets

- Safety Set: patients receiving at least one dose of treatment. Patients will be analyzed according to the treatment actually received. The Safety Set will be used for all analyses of safety endpoints unless specified otherwise and for the summaries of patients in listings related to dosing of study drug.
- Efficacy sets:
  - mITT Set: All randomized patients receiving at least one dose of treatment and have at least one valid stool collection and CFA post baseline while receiving their assigned study drug. The mITT set is considered as the primary set for the efficacy analysis. The mITT set will be used for all analyses of efficacy endpoints.
  - Per Protocol Set: Subset of the mITT set comprising all patients who do not violate the terms of the protocol in a way that would affect the study outcome significantly, as determined by the study clinician. Protocol deviations will be captured throughout the study and classified as minor or major and reviewed at a data review meeting before database lock. Attendees will include appropriate individuals from the Sponsor and contract research organization. Each major deviation will be categorized as either important or not important with respect to the effect on the primary endpoint analysis. A sensitivity analysis will be performed in the Per Protocol Set.

### 10.4 Handling Missing Data

Missing data will not be replaced.

### 10.5 Demographic, Other Baseline Characteristics and Medication

Demographics, other baseline characteristics, and medications will be summarized for the Safety Set unless specified otherwise.

#### 10.5.1 Patient Disposition and Withdrawals

The following will be summarized:

- Number of screen failures
- Number of patients included in the ITT, and PP sets
- Number of patients who completed the study (both treatment periods)

- Number of patients who discontinued the study early with reasons

The patient disposition, inclusion and exclusion criteria not met, eligibility for each analysis set, and protocol deviations will be listed.

### **10.5.2 Demographic and Other Baseline Characteristics**

Demographic and other baseline characteristics will be summarized in the Safety Set:

- For each treatment arm (i.e., 2240 mg/day and 4480 mg/day)
- for each sequence of each crossover
- for each crossover
- for all patients

## **10.6 Safety Analysis**

Safety (AEs, SAEs, discontinuations due to adverse events, and safety laboratory values) will be assessed by descriptive methods. A DSMB will be in charge to assess the safety of MS1819. The DSMB Chairperson will receive SAE reports in real time during the study. In addition, the DSMB will do a full data review at the end of the study to assess overall safety.

## **10.7 Efficacy Analysis**

### **10.7.1 Primary Efficacy Endpoint**

The primary efficacy endpoint is defined as the CFA assessed at the end of each 3-week treatment period (Visit 6 or Visit 9). CFA will be calculated as follows:

$$\text{CFA (\%)} = 100 ((\text{fat intake (g)} - \text{fat excretion (g)}) / \text{fat intake (g)})$$

### **Primary Analysis:**

The primary analysis of the primary endpoint will be a comparison of the mean CFAs from the MS1819 treatment vs the PERT treatment, using descriptive statistics. This analysis will be conducted for each of the two MS1819 doses.

An exploratory analysis of non-inferiority between the MS1819 and PERT groups will be conducted. The treatment effect, along with the 95% confidence interval of the difference in CFA (MS1819 minus porcine PERT), will be estimated. Non-inferiority will be claimed if

the lower bound of the 95% confidence interval is greater than -15%, where 15% is the non-inferiority margin.

Subgroup analyses: Analyses of CFA considering the same approach used for the primary analysis will be performed in the following subgroups:

- by CFA level while receiving porcine PERT (<80% vs ≥80%). An analysis will be done in the subgroup of Patients with CFA below 80% while receiving porcine PERT, as well as in the subgroup of patients with CFA of 80% or greater while receiving porcine PERT.
- by those receiving versus not receiving gastric acid suppression.

### **10.7.2 Secondary Efficacy Endpoints**

Coefficient of nitrogen absorption (CNA) will be calculated and analyzed in the same manner as CFA.

Stool weights, signs and symptoms for malabsorption, body weight, BMI and lipid soluble vitamins (A, D, E, and K), will be analyzed using descriptive methods.

## **11. EXTENSION PHASE**

### **11.1 Exploratory Objective**

The exploratory objective of the Extension Phase (EP) is to find a dose of MS1819 in immediate release capsules that is safe and results in CFA values in a therapeutic range.

### **11.2 Rationale and Dose Justification**

The objective of the OPTION 2 study was to utilize an enteric capsule for MS1819 enzyme delivery in order to provide gastric protection against acid deactivation. Based upon in vitro studies, an expected 50% or more of inactivation of MS1819 might occur in the gastric phase if unprotected. The primary clinical endpoint for the study was to achieve consistent CFAs in the range considered by regulatory authorities and clinical experts to indicate an adequate nutritional supplement for fat digestion.

The results of OPTION 2 may not achieve the stated objective. As in the previous OPTION study, (see section 5.6.3 of this protocol), no safety issues have occurred in the OPTION 2 study. An expert in gastric physiology and gastric emptying has been consulted to understand possible mechanisms that may cause less than expected efficacy with the enteric capsules. In summary, it appears that asynchronous gastric emptying between the meal and the capsules is most likely the problem. Thus, upon eventual dissolution in the duodenum, the MS1819 lipase may not be exposed to much of the meal contents which have already passed beyond the duodenum.

It is clear, that while rational, the enteric capsule may not be performing to expectations. The Extension Phase of our clinical trial, described in this amended protocol, is intended to explore a different approach to solve the problem of delivering an adequate enzyme dose for meal digestion. The use of immediate release capsules, as was the case in the original OPTION trial, provides for immediate dissolution and mixing with the meal in the stomach. In this Extension Phase, we propose to overcome the partial loss of enzyme activity from stomach acid exposure by increasing the dosage of the immediate release formulation. Having the previous experience with the 2.2 grams/day dose in the original OPTION trial, we now propose to increase the dose to 4.4 grams/day, and if safe but not resulting in adequate CFAs, proceed to 6.7 grams/day dosing. Past experience showing a dose response in chronic pancreatitis patients (MS1819/16/01 Phase 2a Study with MS1819) offers encouragement that a higher dose accompanied by satisfactory mixing with meal contents will result in meeting our objective of achieving CFAs in a therapeutic range. The Data Monitoring Committee for the original OPTION study has reviewed the safety profile for the 2.2 grams/day dose in immediate release capsules and approved increasing the dose to 4.4 grams/day.

### 11.3 Extension Phase Study Design

This will be an open label, dose ranging study using an adaptive design. One and potentially two doses of immediate release MS1819 capsules will be studied. Given that we now have a large cohort of patients studied while using a stable dose of PERTs in OPTION and OPTION 2 we will not enroll further PERT control patients.

[figure not shown]
Patients enrolled into the extension phase (EP) will be composed of patients who have completed the crossover phase of OPTION 2. These patients must continue to comply with the same inclusion and exclusion criteria as used in the crossover phase of the OPTION 2 trial (some screening tests may need to be repeated and all subjects must have completed an End of Study visit in the crossover phase). Concomitant medications will be allowed as in the crossover phase. The Drug Product, immediate release capsules each containing 140 mg of MS1819, will be the same as used in a previous OPTION trial (AZ-CF2001) of MS1819 in patients with EPI due to CF.

The EP will first enroll 9 patients, each receiving 4.4 grams/day of immediate release capsules of MS1819, for 2 weeks. At the end of 2 weeks, patients will enter confinement for a controlled diet, stool collection and CFA measurement. Data will be analyzed using descriptive statistics. Based upon resulting CFA data, 5 additional patients may be enrolled at the 4.4 grams/day dose to better characterize the CFA following encouraging results from the initial 9 patients. If safety is satisfactory and the CFAs do not achieve values considered to be in the therapeutic range, 9 more patients will be enrolled and dosed at 6.7 grams/day for 2 weeks. These 9 patients may be patients who have participated in the 4.4 grams/day dose evaluation, as described above, or may be new patients from the OPTION 2 crossover phase. After treatment with 6.7 grams/day for 2 weeks is completed, CFAs will be measured, and data assessed as before. Depending on CFA analysis, either another 5 patients will be enrolled at the 6.7 grams/day dose to better characterize encouraging initial results, or the study will be terminated.

Safety will be evaluated by the DMC Chairperson after the initial 9 patient phase of 4.4 grams/day, and again after the initial 9 patient phase of 6.7 grams/day, should that dose be studied.

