## 5.7 Rationale and Dose Justification

Past *in vitro* studies have shown MS1819 to be relatively acid stable when compared to porcine derived lipases (see Investigator Brochure). However, it is also evident that below pH 4.0, there is increasing inactivation of MS1819 as the pH drops. Work by Gelfond, et al (2013), has shown that in CF patients, the pH in the upper duodenum may be as low as 3.5 for a short period, and the pH in the stomach could be even lower. The gastric emptying time of liquid or solid food may range from 1h-4h or longer and without any gastroprotection MS1819 is likely to have been exposed to low pH in patients with or without gastric acid suppression. Given that in the OPTION study, mean CFA with a dose of 2240 mg/day was 56%, a level below our target of 80%, it may be important to provide more protection of MS1819 against acid inactivation in the stomach and upper duodenum to provide adequate MS1819 dose and optimal lipolytic activity in the duodenum. Accordingly, for this study, enteric capsules will be employed for our MS1819 delivery. Intrinsically enteric capsules

provide API protection against degradation in the gastric environment. The capsule dissolution characteristics of enteric capsules filled with MS1819 show lipase availability at pH 5.5 and above, and no lipase release below pH 5 i.e. adequate gastroprotection. This matches nicely with our peak enzyme activity at pH 6 and allows release in the duodenum where digestion is taking place.

Also, given that our goal is to reach CFA values of 80% or greater, it is reasonable to employ a higher dose than that used in the OPTION study. While it is possible that simply adding the protection of an enteric capsule will provide adequate MS1819 delivery at the 2240 mg/day dose, it is also possible that a higher dose will still be necessary. To explore each of these possibilities, we will use both the 2240 mg/day as well as the 4480 mg/day dose in this study.

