The EP will first enroll 9 patients, each receiving 4.4 grams/day of MS1819, for two weeks. At the end of 2 weeks, patients will enter confinement for a controlled diet, stool collection and CFA measurement. Data will be analyzed using descriptive statistics. Based upon resulting CFA and safety data, 5 additional patients may be enrolled at the 4.4 grams/day dose to better characterize the CFA following encouraging results from the initial 9 patients. If safety is satisfactory and the CFAs do not achieve values considered to be in the therapeutic range, 9 more patients will be enrolled and dosed at 6.7 grams/day for 2 weeks. These 9 patients may be patients who have participated in the 4.4 grams/day dose evaluation, as described above, or may be new patients from the OPTION 2 crossover phase. After treatment with MS1819 IR 6.7 grams/day for 2 weeks is completed, CFAs will be measured, and data assessed as before. Depending on safety and CFA analysis, either another 5 patients will be enrolled to better characterize encouraging initial results, or the study will be terminated.

Safety will be evaluated by the DMC Chairperson after the initial 9 patient phase of 4.4 grams/day, and again after the initial 9 patient phase of 6.7 grams/day, should that dose be studied.

A study flow chart is presented in Appendix 13.1 for the crossover phase and 13.2 for the extension phase, and a schedule of events is presented in Appendix 13.3 for the crossover phase and 13.4 for the extension phase.

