### 4.1 Modified Intent-to-Treat Population

The modified intent-to-treat (mITT) population for the crossover phase includes all randomized patients receiving at least one dose of treatment and having at least one valid stool collection and CFA post baseline while receiving their assigned study drug..

The mITT population for each stage of the extension phase includes all enrolled patients receiving at least one dose of treatment and having a valid stool collection and CFA during the relevant stage of the extension phase.

A stool sample will be considered valid if the date and time associated with the second blue dye marker is recorded, indicating that the stool sample collection is complete.

The mITT population will be used for efficacy analyses. Subjects will be analyzed according to the treatment group to which they were randomized for the crossover phase, regardless of the actual treatment received, unless stated otherwise.

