### **9.2.3 Extension Phase: Exploratory Efficacy Analyses**

All efficacy analyses in the extension phase will be exploratory in nature as the extension phase is dose-finding and not intended to be powered for efficacy analyses. All exploratory efficacy analyses for the extension phase will be descriptive.

All exploratory efficacy analyses will be presented separately for each dose of the extension phase.

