#### **9.2.3.1 Coefficient of Fat Absorption**

The exploratory endpoint of CFA will be assessed at the end of the 2-week treatment period (Visit 13 for the 4.4 grams/day dose or Visit 16 for the 6.7 grams/day dose). CFA is evaluated by the 72-hour marker-to-marker stool sample collection (1 measure at Visit 13 and 1 at Visit 16) and standardized high-fat diet during each supervised confinement. CFA is collected and calculated as described in Section 9.2.1.

CFA at the end of the treatment period (Visit 13 or Visit 16) will be summarized for using descriptive statistics.

The descriptive summary of CFA at the end of the treatment period (Visit 13 or Visit 16) will also be provided using the per-protocol population.

In addition, CFA at the end of the extension treatment period (Visit 13 or Visit 16) will be compared against each the CFA at the end of the PERT crossover study period and CFA at the end of the MS1819 study period for the subset of subjects participating in the extension phase using descriptive statistics.

Fat consumed (g/24h), fat excreted (g/24h), and CFA (%) will be listed by visit for all subjects in the mITT population.

Details of each supervised confinement, including controlled diet and marker-to-marker stool collection, will be listed for all subjects in the mITT population.

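### For an extension dose expanded from 9 to 14 patients, show CFA for the first 9, the added 5 and all 14, because the mean of the 14 tends to overstate CFA once expansion has happened

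*Protocol*

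**What the plan says.** Protocol 11.3 sets up each extension dose in two steps. For the lower dose, "The EP will first enroll 9 patients, each receiving 4.4 grams/day of immediate release capsules of MS1819, for 2 weeks". Expansion then depends on the result: "5 additional patients may be enrolled at the 4.4 grams/day dose to better characterize the CFA following encouraging results from the initial 9 patients". For the higher dose the choice after the first 9 is "either another 5 patients will be enrolled at the 6.7 grams/day dose to better characterize encouraging initial results, or the study will be terminated".

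SAP 2.2 adds safety to the trigger: "Based upon resulting CFA and safety data, 5 additional patients may be enrolled at the 4.4 grams/day dose". SAP 2.4 names CFA only. Neither document gives a number for an encouraging result or for the therapeutic range. The one numeric CFA goal is in Protocol 5.7, where "our goal is to reach CFA values of 80% or greater". That sentence belongs to the rationale for the enteric-capsule crossover and is not tied to the extension's expansion rule.

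On analysis, SAP 4.1 says "The mITT population for each stage of the extension phase includes all enrolled patients receiving at least one dose of treatment", with the further condition of a valid stool collection and CFA in that stage. SAP 7 and 8.1 use stage to mean the dose level, so the first 9 and the added 5 fall in one set. SAP 9.2.3 says "All exploratory efficacy analyses will be presented separately for each dose of the extension phase", and SAP 9.2.3.1 says "CFA at the end of the treatment period (Visit 13 or Visit 16) will be summarized for using descriptive statistics". The visible text plans no split by cohort and gives no caution about the expansion rule. Pooling the 14 is therefore an inference from these rules, not something the SAP states outright.

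**The concern.** A dose reaches 14 patients only if its first 9 looked good. Some of that good result will be chance, and those 9 patients stay in the summary. The added 5 were not part of the decision, so on average they fall back to the true mean. A single column for the dose hides that fall.

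The extension's objective is to find a dose whose CFA is in a therapeutic range, and an expanded dose is the natural candidate. If its true mean lies at or a little below the range, the reported mean may suggest that it is inside. SAP 9.2.3.1 also plans a descriptive comparison of extension CFA with the same patients' crossover CFA on PERT and on MS1819, and that comparison would carry the same conditional bias.

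**Working it through.** The documents state no figure to reproduce: the 9 + 5 sizes come without an SD, threshold, precision target or power.

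**Inputs**
- First cohort 9, added cohort 5, total 14 (Protocol 11.3).
- Cut-off c = 80% on the first-9 mean. This is an assumption: the value is borrowed from Protocol 5.7, and a sharp cut-off on the mean is a simplification.
- SD of CFA 15 to 25 points, centre 20. This is also an assumption. Protocol 5.6.3 reports a range of 7% to 92% on MS1819 in the previous trial, which 32 patients completed; (92 - 7)/4 is about 21.
- True mean μ varied from 75 to 90.

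**Formulas.** Let se = SD/√9 = SD/3, k = (c - μ)/se, and P = 1 - Φ(k), the chance of expansion.
- Bias of the first-9 mean, given expansion: se·φ(k)/P.
- Bias of the 14-patient mean, given expansion: (9/14)·se·φ(k)/P.
- Bias of the added-5 mean from the expansion rule: 0.
- Bias over all outcomes, reporting 14 if expanded and otherwise 9: -(5/14)·se·φ(k).

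**Worked case.** With μ = 80 and SD 20: se = 6.67, k = 0, φ(0) = 0.399, P = 0.5. The first 9 are biased by 6.67 × 0.399/0.5 = +5.32. The 14 are biased by (9/14) × 5.32 = +3.42. Over all outcomes the bias is -(5/14) × 6.67 × 0.399 = -0.95.

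**Range, SD 15 / 20 / 25**

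| True mean | Chance of expansion | Bias of the 14, given expansion | Bias over all outcomes |
|---|---|---|---|
| 90 | 98% / 93% / 88% | +0.18 / +0.59 / +1.18 | -0.10 / -0.31 / -0.58 |
| 85 | 84% / 77% / 73% | +0.92 / +1.67 / +2.46 | -0.43 / -0.72 / -0.99 |
| 80 | 50% / 50% / 50% | +2.56 / +3.42 / +4.27 | -0.71 / -0.95 / -1.19 |
| 75 | 16% / 23% / 27% | +4.90 / +5.69 / +6.51 | -0.43 / -0.72 / -0.99 |

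A simulation with SD 20 and the cut-off at the true mean (300,000 runs, normal data) gave +5.3 for the first 9, +3.4 for the 14, 0.0 for the added 5 and -0.9 over all outcomes. With CFA bounded to 0-100% (beta data) it gave +5.2, +3.3, 0.0 and -1.0.

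**Which figure is closer to the truth?** Given expansion, the mean squared error of the 14-patient mean is (9/14)²·se²·(1 + k·φ(k)/P) + (5/14)²·SD²/5. With μ = 80 and SD 20 this is 0.413 × 44.4 + 0.128 × 80 = 28.6, so the root is 5.35. For the added 5 alone it is 20/√5 = 8.94. With μ = 75 and SD 20 the figures are 6.85 and 8.94. The 14-patient mean has the smaller error in every cell of the table. Only at a true mean of 70 does this start to reverse (8.07 against 6.71 at SD 15, and 9.05 against 8.94 at SD 20), and expansion then happens in just 2% and 7% of cases.

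**Precision of the added 5.** The 95% half-width at SD 20 is 2.776 × 20/√5 = 24.8 points.

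**The case against.** The strongest reply is that the phase claims little. Protocol 11.6.1 and SAP 9.2.3 call it exploratory, dose-finding and not powered for efficacy. All its efficacy analyses are descriptive, and no test or success claim rests on this mean. At a true mean of 80 and SD 20 the conditional bias (3.4 points) is below the nominal standard error of a 14-patient mean (20/√14 = 5.3). Individual CFA values will be listed, so the split could be made later, and the table specifications are a separate attachment that may already contain it. All of this stands, and it is why the priority is low. It does not remove the case for the split, because in a descriptive phase the point estimate is the main product and a prespecified split is more credible than one made afterwards.

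The size also rests on a model. Expansion at 4.4 g/day is discretionary, SAP 2.2 brings safety into it, and nothing ties it to a mean above 80%. That stands too: the figures show a plausible range and do not predict the bias.

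A reader might infer three stronger things that do not follow:
- *That pooling the 14 causes the bias.* It does not. The bias comes from the 9 patients on whom the decision was made, and adding the 5 removes 5/14, or 36%, of it.
- *That the design overstates CFA in general.* It does so only given expansion. Over all outcomes the bias is slightly negative.
- *That the added 5 give the estimate to rely on.* They are free of bias from the expansion rule, but their mean is usually further from the truth than the mean of the 14. They are also later, non-randomised, open-label enrolees, so other differences between the cohorts are possible.

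**Conclusion.** The point holds as a conditional reporting bias. Once a dose has been expanded, the planned per-dose CFA summary tends to overstate the true mean, and nothing in the visible SAP text lets the reader see it. Under the assumed 80% cut-off on the first-9 mean and SD 15 to 25, the overstatement is small for a dose truly above the goal (+0.2 to +2.5 points at true means of 85 to 90). It is moderate at the goal (+2.6 to +4.3) and largest below it (+4.9 to +6.5 at 75), where expansion is uncommon. The calculation does not model patients who take part at both extension doses. This is a low-priority improvement and does not call for a change in design, sample size or conduct.

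**What to change.** In SAP 9.2.3.1, for any dose that is expanded, report CFA in three columns (initial 9, additional 5, all 14), each with a 95% confidence interval. Keep the 14-patient column as the main summary. Add a note that the 14-patient mean is conditional on expansion and tends to overstate CFA, that its nominal interval does not correct for this, and that the additional 5 are free of bias from the expansion rule but imprecise (about ±25 points at SD 20). Attach the same note to the planned comparison with crossover CFA.

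The cost is two extra table columns and a short note, with no new data. The downside is that the column of 5 is imprecise and could be over-read, which is why the 14 should remain the main figure.
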